## SECTION 2: PROJECT DETAILS

### 2.1

Please provide a summary of the project in **non-specialist terms** that could be understood by **non-scientist members of the public**, which includes a description of the scientific background to the study (existing knowledge), the scientific questions the project will address and a justification of these. Please note that the description must be sufficient for the committee to take a reasonable view on the likely scientific rigour and value of the project

This study investigates the effect of fat level, fat type and fat structure, in a food emulsion, on satiety in subjects characterised by their reduced fat and mouthfeel perception (i.e., hypotasters). We propose that by modifying fat delivery, and level of free fatty acids (FFA) in a reformulated food we can reduce the gap between sensory expectation and gut/brain feedback signalling, leading to greater satisfaction (satiety and sustained hedonic response) and long term intake of low fat foods.

We have already submitted a school ethics application for the pilot study and received a favourable opinion to proceed (School of Chemistry, Food and Pharmacy, 14\_17). This previous ethics application covered the recruitment of 80 participants for a series of studies and the experimental procedures for the first phase of the study. The first phase was conducted in a sub-group of 40 "hypotasters" (Group 1) using a food emulsion system (a mayonnaise). There were 3 stages in the pilot study.

- Stage 1, Screening and Characterising Volunteers
- Stage 2, Establish Sensory Tolerance in Expected Satiety of a fat reduced emulsion model (mayonnaise).
- Stage 3, Establish Mouth Gut Discordance of a fat reduced emulsion model (quantified as the discrepancy between expected satiety from sensory signals and measured satiety through a preload consumption study).

Specifically, we characterised participants' oral fat and mouthfeel sensitivity. Participants with reduced sensitivity (i.e "hypotasters") were invited to the second visit of the pilot study for detailed quantification of expected satiety and mouth-gut discordance, following consumption of the mayonnaise food model. Within the pilot study we asked permission from all participants to contact them again for this subsequent UREC approved study, too which they agreed.

This main study involves a different food matrix, a snack product (solid food model) rather than a mayonnaise. In this proposed study, only newly recruited volunteers (N=~25) will undergo Stage 1 Screening and Characterisation, participants already recruited to pilot study will undergo Stage 1 **Screening only'**

**NOTE : All subjects will undergo screening for this study (ie whether they were part of the pilot study or not)**

Stages 2 and 3 of the main study are very similar to pilot study except that a snack product will be used instead of the reduced fat emulsion (mayonnaise) model. Finally, in stage 3, we will also take blood samples from the volunteers for measurement of satiety biomarkers that were not required in the pilot study.

*(This box may be expanded as required – **Word Limit Maximum 250**)*

### 2.2

#### **Procedure**

Please describe concisely what the study will involve for your participants and the procedures and methodology to be undertaken (*you may expand this box as required*).

**Screening:**

For all volunteers that consent to have blood samples (approximately 22 ml, 6 times per visit day via cannulation) taken we will screen them for anaemia, normal liver and kidney function and exclude those with type 2 diabetes. Therefore, a small blood sample will be taken by venepuncture (by the research nurse or trained phlebotomist). The blood sample will be analysed for blood lipids, glucose, full blood count (including haemoglobin), and markers of kidney and liver function. If found to be eligible for the study, the participant will be contacted to confirm their agreement to participate in the study. If any of the screening results are found to be abnormal, these will also be reported to the participant and their GP (Appendix K).

Basic anthropometric measurements (height, weight, blood pressure and body composition (bio-impedance) will be taken for each volunteer.

**Inclusion criteria:**

Men and women

Aged 18-70 years

BMI: 23-32 kg/m^2

Fasting glucose < 7 mmol/l

Fasting total cholesterol < 7.5 mmol/L

Fasting triglycerides < 2.3 mmol/L

Weight stable in the last three months

**Exclusion criteria:**

Diagnosed with diabetes or cardiovascular disease (e.g. stroke or heart attack), gastrointestinal (e.g. IBS, inflammatory conditions, gastroenteritis), endocrine or renal diseases

Smoker

Taking prescribed medications that could influence study outcomes (e.g. lipid lowering medications, anti-depressants, anticoagulants)

Food allergies (e.g. gluten, dairy) and intolerances (e.g. lactose)

Drug abuse

Anaemia (men: haemoglobin<130 g/L and women <115 g/L)

Hypertension (systolic blood pressure > 140 mmHg, diastolic blood pressure > 90 mmHg)

Planning or currently on a weight reducing programme

Pregnancy, planned pregnancy in the next year or lactating

Currently taking part or participation in other research studies within the last three months

There are 3 stages to the study:

**Stage 1, Characterising Volunteers**

**Note : this has already been completed for the majority of volunteers through the pilot study as discussed above. Therefore this stage 1 is needed to recruit a further 25 volunteers for the main study. This wording for Stage 1 is identical to the study already proceeding under school ethics (study 14\_17).**

Volunteers will be characterised on their ability to taste fatty acids. Fat is perceived through three sensory modalities;

mouthfeel, taste ("oleogustus") and odour. Humans vary in their perception of fat across all three sensory modalities. Historically, focus has been on mouthfeel differences. Response to fatty mouthfeel is through trigeminal receptors which are predominantly located around the papillae structures on the tongue. Therefore, papillae density has been found to be correlated to fat-mouthfeel perception. However, there is also inter-individual variation in sensitivity to the oleogustus response. Evidence from several studies suggests that subjects that have low oral sensitivity to free fatty acids (hypo-sensitive) have a higher intake of fatty-foods.

We hypothesise that differences in oral sensitivity to FFA may be related to variation in post ingestion feedback as it is the FFAs that are signalling as metabolites further down the GI tract. Subsequent studies will incorporate hyper- and hypo-sensitive subjects; however in this first study we will focus on hypo-sensitive subjects as we need to establish the differences in fat content that lead to a change in satiety; if we did this with a hyper-sensitive group we may have selected a fat level difference that is not noticeable to hypo-sensitive subjects.

**Aim :** the overall aim was to recruit 80 subjects and identify 40 subjects that have hypo-oleogustus sensitivity and 40 that are hypersensitive. We have recruited 55 subjects to date. In this main study we require a further 25 volunteers.

#### **Methods:**

1. **Fatty Acid Taste Sensitivity.** We use a range of concentrations of oleic acid (a monounsaturated fat found in oils such as olive oil) in milk. Food grade thickener (starch and gum blend) and liquid paraffin are used at low levels to mask texture and lubricity. We use a discrimination forced choice test (a 3-AFC test) where the participant is asked to state the odd sample out of a set. Participants expectorate (spit) the samples into a provided spittoon. Testing is done under red light to mask the visual difference. Participants wear noses clips to avoid the olfactory sensation. (This test has been used successfully in a previous study UREC 12/04). Approximate time to complete: 10 min.
2. **Mouthfeel Sensitivity.** We will test participants for mouthfeel sensitivity but participants are not screened on this basis. A mouthfeel discrimination test will be carried out using savoury biscuits which are constant in overall fat content but vary in mouthfeel characteristics. Five samples will be prepared varying in mouthfeel and participants will be asked to taste the samples and then rate them for a small number of mouthfeel attributes (e.g. Crunchiness, Hardness, Greasiness). Approximate time to complete: 10 min.
3. **Tactile sensitivity testing using Von Frey filaments.** These monofilaments have previously been used to evaluate tactile sensitivity on the tongue, and to relate this to taste sensitivity. Participants will be asked to wear a blindfold, the middle of their tongue is then either stimulated or not stimulated with two Von Frey filaments of different sizes. The participant responds to say whether they have felt the stimulation and how sure they are (signal sure, signal not sure, no signal sure, no signal not sure). This is repeated 30 times in rapid succession. Responses are analysed using an R-index (%) value which is standard for a signal-noise detection test. Approximate time to complete: 10 min.
4. **Mouth behaviour test (Appendix F).** Consumers differ in their mouth behaviour; their preferred method of oral processing. A simple short questionnaire will be used, which has been validated in the USA, to categorise people as Crunchers, Chewers, "Suckers" and "Smooshers". Whereas chewers tend to chew foods to a fine particle size before swallowing, crunchers rapidly crunch and swallow. Such differences not only effect texture perception and preference, they may also effect fat release and fat perception. Approximate time to complete: 5 min.
5. **Fungiform papillae (FP) density.** In order to determine FP density on the tongue, a digital camera will be used to record an image of the number of FP in two one cm^2 areas of the tongue. A small area of the participant's tongue will be temporarily dyed blue using food colour applied by a cotton wool bud. The tongue will then be blotted dry to remove excess moisture prior to recording a digital image. The blue colour will fade after approximately 1 hour and the extent of the colouration is similar to eating certain coloured sweets (e.g. blue Smarties). FPD will be measured as it relates to both mouthfeel sensitivity, as the trigeminal are wrapped around papillae, and taste sensitivity (the taste buds are held within papillae). Approximate time to complete: 5 min.
6. **Genotyping.** We will investigate genes related to sensory perception and food intake.

Genes related to sensory perception will include, but are not limited to, *CD36*, *CA6* and *TAS2R38*. *CD36* is a fatty acid translocase and variation in single nucleotide polymorphisms (SNPs) for *CD36* have been related to

differences in fat perception and fat liking in previous studies. *CA6* is related to production of papillae and taste cells and, therefore, SNPs of *CA6* have been related to differences in mouthfeel and taste sensitivity. The gene most frequently associated with Taste sensitivity is *TAS2R38* and although this is primarily linked to bitter taste, it will be included in order to compare results from this study to previous literature.

Key target genes related to food intake via either gut hormone release or reward will also be genotyped (key genes here will include, but are not limited to, *FTO*, *CNR1* and *DAT1*). *FTO* gene, the gene that encodes the fat mass and obesity-associated protein (also known as alpha-ketoglutarate-dependent dioxygenase) is associated with energy intake but not reward. *CNR1* gene encodes the Cannabinoid Receptor type 1 (CB1) which facilitates the release of the gut hormone ghrelin, causing appetite stimulation. *DAT1* is the dopamine transporter gene encoding for dopamine release and influencing reward mechanisms, polymorphisms in *DAT1* have been associated with overeating. Only genes related to sensory perception, gut hormone release and food reward mechanisms will be investigated.

Buccal cell will be collected from the inside of the participants' mouth using proprietary swabs. The swabs will be used for subsequent DNA extraction. Characterisation of all the taste receptors' genotypes will be determined by SNP genotyping using reverse transcription-polymerase chain reaction (RT-PCR). Volunteers will be given a Gene Fact Sheet (see Appendix E). Approximate time to complete: 5 min.

7. Screening for eating behaviour disorders and restrained eating. We will use the SCOFF questionnaire to screen out any participants with eating behaviour disorders and the 3-Factor Eating Questionnaire to categorise participants by restrained eating (Appendices I and J). Although the former is a screening question we will still do this at the end of visit 1 (stage 1) as we do not want the answering of these questions to influence behavioural responses. We will use the personality trait questionnaire (Big Five Inventory) (Appendix I) as personality may influence eating behaviour, but also to ensure that we do not have a bias of personality types between volunteers that consenting to taking of blood samples and those that opt-out of blood sampling.

## **Stage 2, Establish Sensory Tolerance in Expected Satiety of a fat reduced snack model.**

**Note: the methodology proposed here is based on the stage 2 of the pilot study (SCFP 14\_17), except that it is testing a fat reduced snack model.**

Reduced fat products are typically reformulated to match the perceived texture and mouthfeel of the original product. Changing fat droplet size in emulsions can alter both expected and actual satiety. This stage aims to quantify sensory tolerance to fat reduction by using emulsion technology developed at the Quadram Institute, Norwich. In this study emulsions will be applied to an expanded snack product (extruded corn snack) in a similar manner to the coating of a commercial product where oil is normally applied to yield a fat content of approximately 32% (w/w) on the final product. As in the pilot study, an emulsification process will be used to incorporate water or gel droplets into the oil phase to reduce the fat content of the product whilst aiming to mimic the physical properties of the oil normally applied. The type of droplets (e.g. Gel in Oil versus Water in Oil droplets) and the proportion of droplets will be varied to create a range of emulsion models of varying reduced fat content. Direct addition of free fatty acid (oleic acid) at levels slightly above the threshold level of the hypertasters will also be included in one of the reduced fat emulsion models.

These snack products will be supplied by Pepsico. Findings will be generic and will also apply to other systems.

**Aim:** To define sensory tolerance; the maximum amount fat can be lowered by without leading to significant changes in expected satiety, fatty perception and/or consumer liking using standardized measures. Learnings from the pilot emulsion study will be used to estimate the maximum fat reduction, so only a limited number of fat levels will be trialled in the snack system, but the influence of free fatty acids and emulsion type can also be tested for effects on perception and expected satiety within the snack model.

### **Method:**

1. The emulsion snack models (maximum of 6 small snack samples) will be presented to subjects in a monadic sequential manner (i.e. one at a time) in a balanced order. After tasting each sample, participants will rate a variety of measures including: hedonic liking, fat perception ("how fatty do you think this product is"), mouthfeel perception (e.g. mouthcoating). Questions that are not relevant to the study hypothesis will also be asked to try to

prevent biasing the participants through focusing them on fat perception (e.g. "how salty" "how strong is the flavour"). Following tasting of each sample, they will also be shown an image of a full portion of the sample (approximately 40 g) and asked to rate expected satiety (e.g. "If you were to consume a full portion of this product (show picture), how full do you think you would feel?" "How long do you think it would be before you felt hungry again?"). Unstructured line scales (visual analogue scales, VAS) will be used, participants will receive training in scale use (see example in Appendix G).

2. For three of the samples, the high fat control, low fat control, and maximum-reduced fat emulsion product, we will examine breakdown of the product in the oral cavity by asking the volunteers to provide expectorated boluses. In each case they will be asked to chew a set amount of snack (e.g. 10 g) for a set amount of time (e.g. 20 s) and then to spit out the sample.

**Output:** These tests will determine the maximum level to which fat can be reduced in snacks without causing a significant difference in expected satiety, fatty perception or liking. This will determine whether the emulsion type and / or the addition of a low level of free fatty acids influences expected satiety, fatty perception or liking. The expectorated boluses will be used to determine the fat distribution and snack breakdown characteristics between the high fat control and reduced fat emulsions as these characteristics may help to explain differences in perception,

**Stage 3, Establish Mouth Gut Discordance of a fat reduced snack model (quantified as the discrepancy between expected satiety from sensory signals and measured satiety through a preload consumption study).**

In the pilot study, we aim to have established mouth-gut discordance by showing that the reduction in delivery of fat in a mouthfeel matched emulsion model leads to rebound hunger and consequent over-eating. The aim now is to demonstrate that the reduced fat snack utilising the emulsion technology and a minor addition of free fatty acid can bridge the discordance gap and not lead to rebound hunger / overeating.

**Method:**

1. Using a standard preload study design, and the same fat-emulsion snack model from stage 2, we will contrast effects of 3 test samples in a balanced cross-over design. The 3 samples are: (i) Positive control with 100% of the applied spray being oil (approximately 13g fat per 40 g snack portion); (ii) Low fat snack model, where the same amount of spray is applied to the snack fat but as the reduced fat emulsion determined in stage 2, and (iii) Negative control with the same % fat reduction as in sample (ii) achieved through lowering the amount of oil sprayed onto the snack base.

As it is a 3-way cross over design, participants need to attend 3 visits. Pre-menopausal women differ in hunger at different stages of the menstrual cycle and will be asked to avoid the week prior to their menstrual cycle.

Menstruating women have two phases: follicular and luteal with ovulation occurring at the end of the follicular phase. A number of studies have reported that women in the luteal phase (low estrogen and high progesterone) have higher caloric intake and consume more carbohydrates than women in the follicular phase (high estrogen but low progesterone); hence we aim to avoid the luteal phase.

2. Participants will attend the Food and Nutritional Sciences(FNS) sensory science centre following an overnight fast (approximately 08:50, volunteers staggered by a few minutes) and given a standard study breakfast of cereal, milk and orange juice. They will be asked to clean their teeth and use a mouthwash (provided by the study team) between 7 and 8 am; this is to standardise mouth care procedures as oral microflora can contribute to oral lipase activity and the breakdown of dietary fats. They will be given the test snack (pre-load study food, approximately 50 g) to consume at +2 hours (approx. 11 am) on each study day. We anticipate that the low-fat snack model with matched sensory expected satiety will have a fat reduction of over 25 % but that this may reach a 60% reduction.
3. Primary outcomes: Hunger and satiety will be measured (by VAS, see example in Appendix H) before breakfast, between breakfast and the pre-load study food, immediately after consumption, and every 30 minutes up to 1 hours post pre-load (approx. 12:00). Three hours after breakfast and 1h post the preload study food participants will be given an ad-libitum pasta meal. An excessive portion size will be given to each participant and they will be asked to eat until full. This is achieved by providing a 500 g portion on one plate and replacing it after 5 minutes

with a second 500g portion plate. Weight of pasta consumed will be measured.

4. Secondary outcomes; Circulating biomarkers of satiety and hunger: Participants will be asked to consent to provide biofluid samples for the determination of biomarkers of satiety and hunger. The study is powered for the preload study differences in ad-libitum intake and not on the circulating biomarkers; therefore, if volunteers expressed a preference to not provide blood samples they will not be excluded from the study, but continue with the behavioural study only. The circulating biomarker data we obtain will help to explain mechanisms behind the study behavioural outcomes and provide data on which future studies can be powered. The following samples will be taken after informed consent (appendix C) is given:
  - a. Blood sample collection: Volunteers who consent to providing blood samples will have a cannula inserted (by the research nurse) in a forearm vein on arrival to the Hugh Sinclair Unit of Human Nutrition each study day. Two fasting samples will be taken (-10 and 0 min respectively) before the test breakfast is given. Blood samples will then be drawn at the following time intervals: Post breakfast, (+15 min, approx. 09:15), before the pre-load snack intervention (+1h45 min, approx. 10:45), post pre-load intervention (+2h5min, approx. 11:05), 30 min post preload (approx. 11:35), prelunch (approx. 12:00), post lunch (approx. 12:30). Hunger and satiety hormones (gastrointestinal hormones) and steroid hormones in the prepared plasma will be measured; these will include but are not limited to ghrelin, leptin, glucagon-like peptide (GLP-1), gastric inhibitory peptide (GIP), cholecystokinin (CCK) and peptide YY (PYY). Estrogen and progesterone will be measured; their ratio can affect caloric intake, but the effect of this ratio on satiety and intake of fat-snacks is not yet known. Endocannabinoids (anandamide and 2-arachidonoylglycerol), known to be lipid mediators, will also be quantified alongside lipidomics using HPLC/MS/MS. Such lipidomics can detect low-abundance 'endocannabinoid-like' (eCBL) bioactive signalling lipids. Plasma triacylglycerol (TAG), non-esterified fatty acids (NEFA) and insulin will also be measured. Nuclear Magnetic Resonance (NMR) Spectroscopy-based metabolomics will be used to profile metabolites in the blood.
  - b. Saliva samples: Non-stimulated saliva samples (1 ml) will be collected at the same 6 time points as for the blood samples. Two types of analysis will be performed; gastrointestinal hormones and metabolomics using NMR. Hormone measurements in saliva are more difficult to quantify than in blood, hence the preference for blood samples; however we aim to compare measurements from the two sample types to provide evidence for future studies and to be able to incorporate data from any volunteers that do not consent to providing bloods. Saliva NMR metabolic profiles provide information on metabolic outputs taking place in the system at a given moment in time. We will use these to investigate whether there is a metabolomics signature that can be determined following consumption of the low and high fat snacks.
  - c. Urine samples: volunteers will be asked to provide one urine sample at home following an overnight fast, and bring into the unit, and one 3.5 hour urine sample to be collected during each visit. (They will be asked to void their bladder at 8.50 and then collect all urine from 08:50 to 11:50 (i.e. pre study lunch) whilst at the Unit). These samples will be also analysed by NMR since urinary NMR metabolic profiles provide information relating to by-products of endogenous metabolic pathways as well as products of microbe-host co-metabolism, thus will aid in identifying potential mechanisms post consumption of low versus high fat snacks.

(Note: All questionnaires or interviews should be appended to this application)

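### The Stage 3 booking rule bars one week before menses, but its stated aim is to avoid the whole luteal phase, so the control is only partly achieved

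*Protocol*

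**What the plan says.** Section 2.2, Stage 3, Method item 1 sets up the comparison: "we will contrast effects of 3 test samples in a balanced cross-over design". Each participant attends once per snack: "As it is a 3-way cross over design, participants need to attend 3 visits".

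The only scheduling rule for pre-menopausal women is that they "will be asked to avoid the week prior to their menstrual cycle". I read this as the seven days before menses. The paragraph after it explains why:

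- **Phases:** "Menstruating women have two phases: follicular and luteal with ovulation occurring at the end of the follicular phase".
- **Effect on intake:** women in the luteal phase are reported to "have higher caloric intake and consume more carbohydrates than women in the follicular phase". No size is given.
- **Conclusion:** "hence we aim to avoid the luteal phase". No early or late part of the phase is singled out.

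Item 4a adds "Estrogen and progesterone will be measured; their ratio can affect caloric intake". These hormones are assayed in plasma, and item 4 lets volunteers decline blood sampling. Saliva (item 4b) is assigned to gastrointestinal hormones and metabolomics. The medical questions in the screening questionnaire ask about menopausal status, contraception and cycle regularity, but no eligibility criterion or booking rule refers to cycle regularity or contraception. The protocol gives no interval between Stage 3 visits, no phase check before a visit, and no instruction to record cycle day.

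**The concern.** The rule and its reason cover different spans of days. If ovulation closes the follicular phase, the luteal phase runs from ovulation to the next menses. A seven-day bar covers all of it only if it lasts seven days or less. Staff who follow the rule exactly can book visits that the same section says it wants to avoid.

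The protocol itself names phase as a nuisance factor for intake and hunger. Both sit under the primary outcomes in item 3 (appetite ratings and weight of pasta eaten), and item 4 says the study is powered on intake. If a woman's phase differs between visits, the phase effect enters her within-person snack contrasts. No cycle information is scheduled at the visits for those who decline blood. This concerns conduct and data capture, so a later analysis plan cannot supply it if nothing is collected.

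**Working it through.** **1. The plan's own figure.** The protocol gives no figure for phase mixing. Its one relevant number is in section 3.1: 38 participants to detect a 20% change in intake. No SD, alpha, sidedness or power is stated, so 38 can be neither reproduced nor refuted. Using n = (SD × (z_alpha + z_power) / delta)² for a paired difference, and assuming two-sided 0.05 and 80% power, the implied SD of the difference is

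20 × √38 / (1.960 + 0.842) = 44.0% of mean intake.

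Other choices give 38.0% (two-sided, 90% power) or 49.6% (one-sided, 80% power). I use 44.0% below.

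**2. Bookable luteal days.** Let C be cycle length and L luteal length, with the last 7 days barred. The luteal share of bookable days is p = (L − 7)/(C − 7). The documents give neither C nor L. I assume C = 28 (range 24–35) and L = 14 (range 10–16).

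- L = 14, C = 28: p = 7/21 = 0.33
- L = 10, C = 28: p = 3/21 = 0.14
- L = 16, C = 28: p = 9/21 = 0.43

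If the rule matched the aim, p would be 0.

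**3. Mixed phases, random visit days.** With three independent bookable days, P(both phases occur) = 1 − p³ − (1 − p)³.

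- p = 0.33: 67%
- p = 0.14: 37%
- p = 0.43: 73%

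Over C = 24–35 and L = 10–16 the range is 29% to 75%. At p = 0.33, P(at least one luteal visit) = 1 − (0.667)³ = 70%.

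**4. Mixed phases, fixed spacing.** Random days are only one possibility. For a 28-day cycle, taking every bookable start day and moving any barred visit to the next allowed day:

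| Spacing | L = 14 | L = 10 |
|---|---|---|
| 7 days | 100% | 43% |
| 14 days | 100% | 29% |
| 21 days | 33% | 14% |
| 28 days | 0% | 0% |

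At 28-day spacing with L = 14 no woman mixes phases, but 33% have all three visits in the luteal phase, so the stated aim is still missed.

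**5. Cost in precision.** If luteal intake differs by d (% of mean intake), the variance added to a within-woman difference with random visit days is v = 2p(1 − p)d². At p = 1/3:

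- d = 5: v = 11.1
- d = 10: v = 44.4, which is 2.3% of 44.0² = 1936
- d = 20: v = 177.8, which is 9.2% of 1936

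These increases apply only to affected women. If a fraction f of participants is pre-menopausal, n becomes 38 × (1 + f·v/1936). Neither d nor f is in the documents, so I assume d = 5–20 and f = 0.25–0.50.

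- Smallest (d = 5, f = 0.25): 38 × (1 + 2.78/1936) = 38.05, rounded up to 39
- Largest (d = 20, f = 0.50): 38 × (1 + 88.9/1936) = 39.74, rounded up to 40

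At the low end, the step from 38 to 39 is almost entirely rounding.

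**The case against.** The strongest reply is that the rule is a reasonable partial control. It needs only a calendar, and under the base assumptions it removes half of a 14-day luteal phase. How wide to make it is partly a design preference. That is fair, but the protocol does not present the rule as partial. It states an aim that the rule does not meet.

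The size of the effect is also open to challenge, and most of that challenge stands. The 67% depends on assumed cycle figures and random visit days, and step 4 shows that spacing matters most. The inclusion criteria admit men and women aged 18–70, with no pre-menopausal share given. Hormonal contraception is not named as an exclusion, and women whose contraception suppresses ovulation would not be affected. A reader might infer that most pre-menopausal women will mix phases. The documents support only that they may.

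A reader might also infer that phase cannot be recovered for women who decline blood. That goes too far. The booking rule already relies on each woman knowing when her period is due, so cycle day can be asked of anyone. The gap is that the protocol does not say it will be asked.

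Finally, the choice of covariates in the intake model commonly belongs to the statistical analysis plan, which is not shown. Its absence from the protocol is no fault.

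**Conclusion.** The mismatch is in the text, and nothing elsewhere in the protocol resolves it. Following the rule exactly leaves luteal days bookable whenever that phase exceeds 7 days, so the control the protocol sets itself is only partly achieved. That part of the conclusion needs no assumption beyond the luteal phase lasting longer than a week.

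How often phases mix is uncertain. It is 67% under the base assumptions with random days, and 0% to 100% across the spacings examined. It applies only to ovulating pre-menopausal women, whose number is unknown.

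Two stronger readings are not supported. The first is that the snack comparison is biased: balanced order spreads phase over the snacks, leaving mainly within-person noise and some chance imbalance. The second is that the study is underpowered for this reason: 39 to 40 still lies within the 40 per taster group planned in section 3.1, although 40 would leave no margin for dropout within one group. The point is modest. It is worth acting on because the protocol names this factor itself and the remedy is cheap.

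**What to change.** 1. In section 2.2, Stage 3, Method item 1, reconcile the booking rule with the stated aim so that both describe the same days. Either the rule is changed to match the aim, or the aim is reworded to say what the rule covers.
2. At every Stage 3 visit, record cycle day for all pre-menopausal women, whether or not they give blood, together with the contraception status already asked at screening. Phase can then be used as a visit-level covariate for intake and the appetite ratings.

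The cost is one amended sentence and one question per visit, with slightly slower booking if the rule is tightened.
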